Other Demographic and Clinical Data: Demographic data will include age, gender, ethnicity, income, marital status, education, employment, and distance from the VA and/or CBOC¹⁰. Diagnosis of anxiety disorders, PTSD, and depression will be based on the MINI structured interview²¹. Each diagnosis will be dichotomized and coded as present/absent. PTSD severity will be assessed using the PTSD Checklist-Civilian Version (PCL-5²²), a standardized self-report rating scale that corresponds to DSM-5 symptoms of PTSD and possess strong psychometric properties. Medical complexity will be calculated using the Charlson Comorbidity Index (CCI) as defined by VA database extractions for the 12 months prior to the baseline date. The Charlson score has been widely used in the literature for assessing morbidity and mortality^{23,24}. Psychotropic medications will be collected through VINCI databases following procedures used

in the team's prior work^{10,11,25}. Medication tracking will include information on start date of medication, dose, and days-supply. Medication use will be coded for presence or absence and changes in type or dosage. We will monitor medications use in both bCBT and EUC groups through database extraction after the 12-month assessments to allow us to determine whether assignment to bCBT affected receipt of medications. Mental health service use: Mental health service use will be monitored for each participant to allow us to control for non-bCBT mental health service use. We will collect data via review of VA medical records as well as from a self-report non-VA service-use questionnaire (Appendix 6G). We will use CDW to capture data on emergency room visits and hospitalizations and will compare the frequency and types of such visits between arms (and between in-person and VVC-H bCBT encounters) quarterly. We will involve clinical leadership and the IRB if there are between-group differences in these safety measures.

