Quantitative data will be collected for 12 months following baseline to allow us to examine the long-term effects of the intervention (see Table 4). An initial telephone assessment will screen for exclusion criteria, with final eligibility determined at the baseline appointment. Four-, eight-, and twelve-month follow-up assessments will be conducted by blinded independent evaluators. Upon completion of the follow-up assessment period, the Veteran will be mailed a Thank You

note (See Appendix 10B) notifying them that their participation in the study is complete and acknowledging their contribution to this research.

Table 4. Assessment Schedule – Effectiveness Aims

	Screen	Baseline	4 mo (post tx)	8 mo F/ U	12 mo F/U
GAD-7	X				
Cog Screen, Demographics, Diversity Supplement, Charlson Index, Attachment, Social Support, Chart Review		X			
MINI – Anxiety, Depression, Mania, Psychosis, Substance use and PTSD modules, Audit-C		X			
GAD-7, OASIS, SF-12V, PCL-5, PHQ-9,		X	X	X	X
Working Alliance Inventory (Patient and Clinician)			X		
Charlson Comorbidity Index – Database Extraction					X
Medication and Health Service Use -- Database Extraction					X

Mixed Methods Exploratory Aim:

We will conduct a mixed-methods formative evaluation (FE), informed by Stetler et al.,³⁵ to evaluate the implementation of the bCBT clinical intervention and VVC-H. The RE-AIM QuEST⁴ framework will inform qualitative and quantitative data collection related to reach, effectiveness, adoption, implementation, and maintenance (see Table 5). We will collect FE data during the study's pre-implementation (Y1 Q1-Q2), implementation (Y1 Q3 – Y3 Q4) and post-implementation (Y4 Q1-4) phases.

Pre-implementation: During pre-implementation, we will conduct semi-structured interviews with the PCMHI clinical director and bCBT champion at each site. Directors and clinical champions will review and provide feedback on the bCBT materials, training materials, provider bCBT delivery procedures, and provider preparedness to deliver exposure in PCMHI. Pre-implementation findings will allow us to refine the bCBT delivery approach, address barriers, and tailor provider support procedures. Consenting of the staff for the pre-implementation interviews will not be warranted as no identifiers will be collected during the interviews.

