Provider Sample. No formal sample size calculations were used for the implementation-focused elements of this project. Rather, the team will invite all CBOC providers at the sites within the Houston, New Orleans, and San Antonio VAMCs to participate and subsequently evaluate how many providers opted to engage in the bCBT project. These procedures are common for implementation-focused trials that often have a smaller pool of "subjects". Designs of this nature

often look less at statistical significance and instead focus more on descriptive quantitative data and depth interviewing and qualitative analyses to determine impact and “lessons learned”.

Data and Quality Assurance:

Independent Evaluation: Outcome data will be collected by independent evaluators (IEs) who will be blinded to randomization. All IEs will be based in Houston, with direct oversight by [name]. IEs will undergo training and calibration on all study measures and be regularly reassessed for quality.

Missing Data: We anticipate that most missing data will be due to attrition (see below). We will examine missing data for bias and conduct sensitivity testing using longitudinal hierarchical mixed models. We will conduct sensitivity analyses using tests for missing completely at random⁴¹ to evaluate whether the reasons for loss to follow-up at the various times are related to observed values of the outcome variables.

Minimization of Attrition: A 25% attrition rate was used for sample size calculations, based on our prior and ongoing psychotherapy trials with Veterans¹⁰. Dropouts will include any participants who indicate a desire to withdraw or are lost to follow-up after randomization. The flexible delivery approach aims to decrease attrition and increase bCBT engagement and adherence. We will also minimize attrition by reducing our “research presence” using telephone assessments, limiting research contact, compensating participants, and allowing bCBT participants who drop out of treatment to continue with research follow-up assessments.

All analyses for the study will occur exclusively at the Houston HSR&D CoE under the direction of the study PIs ([name] and [name]) and study data analyst ([name]).

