6.0 Reporting

- Include procedures for reporting unanticipated problems, serious adverse events, and protocol deviations.
- Include information about whether the study has a Data Monitoring Committee and if so, how often it will meet.

All unanticipated serious adverse events (U-SAEs) and unanticipated serious problems (UAPs) will be reported to the VA Central IRB within five business days. U-SAEs will be reported to VA Central IRB regardless of their relationship to the research. All protocol deviations, violations, and/or noncompliance will be reported to the VA Central IRB within five business days of the reporting individual becoming aware of the occurrence.

Safety information, including SAEs/UAPs, that will be collected:

During completion of the study assessment timepoints the participants mental health will be accessed via questions administered. Participants demonstrating increased mental health distress, based upon responses to the assessment, will be evaluated and referred for additional assessment and intervention as needed. Participants in need of immediate treatment (e.g., active psychosis or suicidal intent) will be referred for appropriate services with VA upon identification. Study staff will follow up on any positive responses to items involving suicidal thinking, using a structured crisis-assessment protocol (see Appendix 5). Participants who express suicidal ideation will be forwarded to a study investigator who will triage and refer for care as appropriate.

All occurrences of events resulting in a participants' death, life threatening experience, hospitalization, prolonged hospitalization, or persistent or significant disability will be documented. Any occurrence of an event that results in the need for medical or other interventions to prevent any of the above listed outcomes will be documented as well. As such, any participants identified as having an immediate mental or physical health issue will be referred to care as appropriate.

Frequency/methods of safety-related data collection:

Collection of safety information will commence when the first participant is enrolled in the study. Safety information may be collected either 1) during baseline and follow up assessments, 2) during bCBT sessions, or 3) during telephone contacts with participants made for purposes of

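### Section 6.0 promises to document every death, but its routes depend on contact and the quarterly database comparison does not name deaths, so deaths after dropout have no stated source

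*Protocol*

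**What the plan says.** Protocol Section 6.0 (Reporting) sets a complete-capture standard: "All occurrences of events resulting in a participants' death, life threatening experience, hospitalization, prolonged hospitalization, or persistent or significant disability will be documented". Under frequency and methods it then gives three routes: baseline and follow-up assessments, bCBT sessions, and telephone contacts made for scheduling. It adds that participants or other informants may volunteer safety information on those occasions. Unanticipated SAEs go to the VA Central IRB within five business days, whatever their relation to the research.

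Protocol Section 5.5, under other demographic and clinical data, contains a separate safety activity: "We will use CDW to capture data on emergency room visits and hospitalizations". The study team "will compare the frequency and types of such visits between arms (and between in-person and VVC-H bCBT encounters) quarterly", and clinical leadership and the IRB are brought in if the arms differ. Just before this, the same paragraph describes chart review and a self-report questionnaire on non-VA service use (Appendix 6G). Their stated purpose is "to allow us to control for non-bCBT mental health service use".

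Table 4 in Section 5.5 has a row "Medication and Health Service Use -- Database Extraction" with one mark, in the 12-month column. It has no row for a quarterly extraction and none for the Appendix 6G questionnaire.

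On attrition, Section 5.6 assumes 25% at one year and defines it broadly: "Dropouts will include any participants who indicate a desire to withdraw or are lost to follow-up after randomization". The SAP text covers the primary-aim analysis and adds nothing on safety data.

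**The concern.** The standard in Section 6.0 is stronger than the means listed beneath it. Each listed route works only while someone is in touch with the participant or with a person who knows them. The safety activity that does not need contact is the CDW comparison, but it names two event types and death is not one of them. No section describes a vital-status check.

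The gap therefore falls on people who are out of contact, where a serious event is hardest to learn about. If a participant dies after contact is lost, the trial could record only a loss to follow-up. The protocol itself describes anxiety disorders as associated with suicide (Abstract and Section 2.0), so mortality is a relevant safety outcome in this population. In addition, an admission first seen in the CDW data has no written path into SAE reporting, because Section 6.0 does not mention that data source.

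**Working it through.** **Step 1: reproduce the attrition arithmetic (Section 5.6, Step 3).** The plan inflates each arm by n/(1 − 0.25).

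- bCBT: 109/0.75 = 145.3; the plan uses 145.
- EUC: 58/0.75 = 77.3; the plan gives 78 and rounds to 80.
- Total: 145 + 80 = 225, as stated.

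**Step 2: number expected to have incomplete research follow-up at one year.**

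- All randomized: 0.25 × 225 = 56.25, about 56.
- bCBT: 0.25 × 145 = 36.25, about 36.
- EUC: 0.25 × 80 = 20.

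**Step 3: set the sources side by side.**

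| Source | Section | Needs contact? | Names deaths? | Listed in 6.0 as a safety source? |
|---|---|---|---|---|
| Baseline and follow-up assessments | 6.0 | Yes | Through the general promise | Yes |
| bCBT sessions | 6.0 | Yes | Through the general promise | Yes |
| Scheduling calls, including informants | 6.0 | Yes | Through the general promise | Yes |
| Quarterly CDW comparison | 5.5 | No | No | No |
| Chart review for service use | 5.5 | No | No | No |
| Non-VA questionnaire (Appendix 6G) | 5.5 | Yes | No | No |

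No row is contact-free, names deaths, and is listed as a safety source.

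**Step 4: timing.** Section 5.5 says that the between-arm comparison is quarterly. Table 4 shows one health-service extraction, at 12 months. Either the Table 4 row is the covariate extraction and the quarterly safety extraction is unscheduled, or the row is meant to cover both and conflicts with Section 5.5. The documents do not say which.

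**Step 5: could a death plausibly fall in this group?** The documents give no death rate, so this is illustration only. With an assumed 12-month risk p, the expected number of deaths among 56 people is 56p, and the chance of at least one is 1 − (1 − p)^56.

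| Assumed p | Expected deaths | Chance of at least one |
|---|---|---|
| 0.5% | 0.28 | 24% |
| 1% | 0.56 | 43% |
| 2% | 1.12 | 68% |
| 3% | 1.68 | 82% |

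These are deaths for which no source is stated, not deaths shown to be missed.

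**The case against.** The case against is substantial and limits what can be claimed.

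- **There is other active safety enquiry.** Suicidal thinking is asked about at baseline and at 4, 8 and 12 months, with structured follow-up of positive answers. The CDW comparison is not the only active safety measure. This stands, but those enquiries also need contact.
- **Chart review is contact-free too.** Section 5.5 plans a review of VA medical records, and bCBT notes are monitored through templates. This stands as a fact. The record review is there to measure mental health service use and the templates to document bCBT treatment; neither is named as a source for deaths or SAEs.
- **CDW coverage is not stated.** A reader might infer that it holds VA care only and that non-VA events are lost. The abbreviation is never expanded and its coverage is not described, so the documents do not support that. Section 6.0 also covers hospital admissions wherever they occur, if they are reported.
- **Dropout need not end extraction.** A reader might infer that events among the 25% are missed. No section says that database extraction stops for people lost to follow-up, participants who stop only bCBT may stay in follow-up, and many of the 56 may have completed month 4 or month 8.
- **Table 4 concerns effectiveness.** Its title refers to the effectiveness aims, and its row may be the medication and service-use extraction planned after the 12-month assessment. A reader might infer that safety is first examined at month 12, but the explicit quarterly wording in Section 5.5 argues against that.
- **Low-risk setting.** The trial compares psychotherapy with enhanced usual care, with suicide triage, SAE reporting and a national DSMB. This lowers the stakes; it does not supply a source for deaths.

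Appendix 6G was not available, and the questionnaire's content and timing may be set there.

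**Conclusion.** The point holds as a gap in stated ascertainment. The plan promises to document all deaths, its listed routes depend on contact, and the quarterly contact-free comparison neither names deaths nor feeds SAE reporting. About 56 of 225 participants (36 bCBT, 20 EUC) are expected to have incomplete research follow-up. This rests on the plan's own 25% assumption and overstates the number actually out of reach at any earlier time. It also includes withdrawals, for whom extraction may no longer be authorized.

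The documents do not show that any event will be missed, that non-VA events are excluded, or that the safety comparison will be late. The difference between Section 5.5 and Table 4 is a matter to reconcile. This is a worthwhile, low-cost improvement to safety ascertainment and does not affect the primary efficacy analysis.

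**What to change.** 1. In Section 5.5, add deaths to the quarterly extraction and to the between-arm comparison. Apply it to all randomized participants whose authorization still allows it, and state explicitly that this includes those lost to follow-up.
2. In Section 6.0, list that extraction as a source for SAE reporting, so that events found there enter the existing reporting route.
3. Reconcile Section 5.5 with Table 4 by giving the quarterly safety extraction its own row or a cross-reference, separate from the 12-month medication and service-use extraction.
4. Show the Appendix 6G questionnaire in Table 4. If it records emergency visits or admissions, count them in the safety comparison.

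The cost is a few more fields in an extraction already planned, a schedule entry for an existing questionnaire, and some review time by current staff. Sample size and the primary analysis do not change.

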5.6 Data Analysis

- Provide sample size determination and analysis (include anticipated rate of screen failures, study discontinuations, lost to follow-up etc.).
- Describe how, where and by whom the data will be analyzed.

Primary aim: Anxiety and Quality of Life differ as a function of bCBT for anxiety vs. EUC:

All analyses will be done on an intention-to-treat basis, and participants will be analyzed in the group to which they were randomized. We will first determine whether participants randomized

to the two study arms differed on baseline characteristics, age, race, gender, medical or mental health comorbidities, and anxiety. Chi-square tests will be used for categorical variables and t-test for continuous and ordinal variables.

We will examine the normality of the distributions of both primary outcomes and will consider transformations such as the log or the inverse. Because we are using an unequal randomization (see sample size section), it is especially important to test the assumption about the homogeneity of the variance of the residuals across the levels of the independent variables³⁷. For analyses of our primary outcomes, we will test the homogeneity assumption before testing for differences between the bCBT and EUC groups. If the assumption of equal variances is violated, we will use statistical tests such as the approximate t-test, which uses individual sample variances instead of the pooled variance. In addition, we will obtain Satterthwaite's approximation of the degrees of freedom. For the regression models, we will test whether the residual variances are equal and, if necessary, we will fit unequal variance models to obtain better estimates of the standard errors of the difference between groups. We will calculate the absolute differences in outcome measures between baseline and 12-month follow-up and the effect sizes of the bCBT group compared with EUC. We will also examine effect sizes for the bCBT group baseline vs. post-treatment and 8-month follow-up.

To compare changes in anxiety symptoms between the two groups over time, we will use a longitudinal, mixed-model analysis containing terms for the intercept, treatment, time, and interaction between time and treatment. In separate analyses, we will compare changes in quality-of-life between the two groups over time using a similar mixed-model approach. The mixed-model analysis will allow us to nest patients by site. Any baseline characteristics found to be significantly different between bCBT and EUC will be included in the model, as will any differences in mental health service use. The four time points (baseline, 4-, 8-, and 12-month) will allow us to assess the immediate impact of treatment and the longer-term retention, improvement, or decay in outcomes. The treatment effect will measure differences between the intervention and control groups at baseline, and the time effect will measure whether there was an overall change over time in the outcome. The term of most interest will be the interaction between time and treatment, which will indicate whether there is a difference over time between the two groups. The use of the random-coefficient model will allow us to fit a line for each participant using his/her available data, including participants with missing values, and maximize the power to detect differences.

Secondary Analyses: Prediction of bCBT response and VVC-H use:

We will run two logistic regression analyses using only data from participants who received bCBT. In analysis 1, we will identify characteristics that predict response to treatment as defined as a reduction of 50% on the GAD-7. Predictor variables will include: baseline anxiety severity (GAD-7 score), presence of specific anxiety diagnoses (GAD, Panic, Social Anxiety, Other), medical comorbidities, and brief CBT-related factors (number sessions received and treatment engagement). In analysis 2, we will identify characteristics associated with VVC-H use. VVC-H

use will be classified as any (one or more VVC-H sessions) or none. Predictor variables will include: age, distance to VA facility in miles, medical comorbidities, depression and PTSD (presence or absence), and Veteran self-reported comfort receiving in-person VHA care and confidence using video-based services and technology.

Implementation Analyses (Exploratory):

Analyses will use data from the mixed-method formative evaluation described above. Qualitative pre-implementation data will be analyzed using rapid qualitative analysis, a systematic and rigorous process, to provide data in real-time to tailor the intervention, and identify contextual barriers prior to rollout^{38,39,40}. Implementation and post-implementation interviews with providers and Veterans will be analyzed using directed content analysis⁴¹ consisting of deductive (a priori) codes from the RE-AIM QuEST framework. Inductive (a posteriori) codes that emerge from providers' and Veterans' experiences with the intervention and VVC-H delivery will also be identified. We will utilize Atlas.ti software to facilitate analysis and management of qualitative data. Quantitative data will be collected and analyzed as descriptive data.

Sample Size and Power Calculations

Primary Aim: To determine whether anxiety symptoms (GAD-7) and quality of life (SF-12) differ as a function of the intervention (bCBT for anxiety vs. EUC) at 4-, 8-, and 12-month follow-ups. A three-step sample-size calculation indicates that 225 anxiety patients will need to be randomized to draw conclusions regarding the primary hypothesis that bCBT will be superior to EUC at 4-, 8, and 12-month assessments.

Step 1: Power to detect GAD-7 differences. A sample size of 138 anxiety patients is needed to detect an effect size = 0.38 for the differences between bCBT and EUC GAD-7 outcomes using a two-sided t-test with 80% power at the .05 significance level, adjusted for repeated measures³⁷. The formula for the sample size, adjusting for repeated measures, is

$$N = \frac{2 * (Z_{(1-\alpha/2)} + Z_{(1-\beta)})^2 [1 + (T - 1) \rho]}{d^2 T}, \text{ where } N \text{ is the sample size per group, } Z_{(1-\alpha/2)} \text{ and}$$

$Z_{(1-\beta)}$ are the $(1-\alpha/2)$ and $(1-\beta)$ percentiles of the normal distribution, T is the number of follow-up measures, ρ is the correlation coefficient of the repeated measurements, and d is the effect size⁴². Solving this with $T = \text{three follow-up measurements after baseline}$, $d = 0.38$, and $\rho = .7$ yields a sample size per group of 69, and total sample $N^t = 138$.

Quality of Life Outcomes. Our prior study of patients with anxiety or depression¹⁰ resulted in mean, standard deviations, and effect size of 7, 11, and 0.3 respectively for the SF12V mental component score (MCS). SAS[®] proc power indicated that a two-sided t-test with 80% power at the .05 significance level requires a sample of 40 patients per group (80 total). Because the sample required for the anxiety measure (GAD-7; $n=138$) is greater than that needed for the

quality-of-life measure (SF12V; n=80), adjusting for repeated measures, unequal sample, and clustering on provider is presented below for the anxiety measure.

Step 2: Unequal Randomization. To increase power for the project's secondary and implementation outcomes and to reduce unnecessary recruitment, unequal allocation will be used where approximately 60% of Veterans will be randomized to bCBT. As noted by Dumville et al.³⁷, an unequal number of participants per group is an under-used technique that offers advantages for randomized trials, most notably, reduction in unnecessary recruitment. Revised total sample size $N' = N(1+k)^2/4k$, where $N=138$ and $k=1.5$, which gives revised total sample $N'=145$. The individual sample size in each of the two groups are $N'/(1+k)$ and $kN'/(1+k)$; giving $n=58$ in the EUC group and $n=87$ in the bCBT group.

Step 3: Provider Inflation Factor. The bCBT sample size was then inflated to account for the intraclass correlation due to clustering of patients within providers⁴³. We also will adjust the sample sizes for both the bCBT and EUC groups to account for attrition. Because only participants receiving bCBT are assigned to a provider, we first determined the average number of bCBT patients per provider (87 bCBT patients/25 providers = 3.5 patients per provider). To account for clustering in the bCBT group, the number of bCBT patients is inflated by the factor $[1 + (\bar{m} - 1) c]$, where \bar{m} is the average number of bCBT patients per provider and c is the correlation among patients seen by the same provider. Based on the sample size of 87 bCBT patients and an assumed correlation among patients of .10⁴³, our inflation factor is 1.25 ($87 \times 1.25 = 109$). Finally, to account for attrition, we assumed an attrition rate at 1 year of 25% ($109 \times (1/0.75) = 145$) gives 145 bCBT patients. A similar clustering inflation factor was not used for the EUC group, as no providers are assigned. Attrition rate of 25% was assigned to the EUC group ($58 \times (1/0.75) = 78$), rounded to 80 for randomization. The final number of randomized patients equates to 225 (145 bCBT and 80 EUC).

Secondary Aims:

Prediction of bCBT response and VVC-H use (bCBT group only). To assess predictors of bCBT response and VVC-H use, at least 10 events per variable in the logistic-regression models are needed to have unbiased estimates of the sample variance of the regression coefficients⁴⁴. No sample-size calculations were conducted for secondary aim, but SAS[®] proc power (version 9.4)⁴⁵ indicated a sample of 145 is adequate for 80% power to test odds ratio of 2.5, and conservative estimates for sample size and assumptions necessary to run the analyses suggest the project will be appropriately powered for 10 variables⁴⁶. Secondary analyses will include 8 variables for aim 2A (bCBT response; model #1) and 8 variables for aim 2B (VVC-H prediction; model #2).

Provider Sample. No formal sample size calculations were used for the implementation-focused elements of this project. Rather, the team will invite all CBOC providers at the sites within the Houston, New Orleans, and San Antonio VAMCs to participate and subsequently evaluate how many providers opted to engage in the bCBT project. These procedures are common for implementation-focused trials that often have a smaller pool of "subjects". Designs of this nature

often look less at statistical significance and instead focus more on descriptive quantitative data and depth interviewing and qualitative analyses to determine impact and “lessons learned”.

Data and Quality Assurance:

Independent Evaluation: Outcome data will be collected by independent evaluators (IEs) who will be blinded to randomization. All IEs will be based in Houston, with direct oversight by [name]. IEs will undergo training and calibration on all study measures and be regularly reassessed for quality.

Missing Data: We anticipate that most missing data will be due to attrition (see below). We will examine missing data for bias and conduct sensitivity testing using longitudinal hierarchical mixed models. We will conduct sensitivity analyses using tests for missing completely at random⁴¹ to evaluate whether the reasons for loss to follow-up at the various times are related to observed values of the outcome variables.

Minimization of Attrition: A 25% attrition rate was used for sample size calculations, based on our prior and ongoing psychotherapy trials with Veterans¹⁰. Dropouts will include any participants who indicate a desire to withdraw or are lost to follow-up after randomization. The flexible delivery approach aims to decrease attrition and increase bCBT engagement and adherence. We will also minimize attrition by reducing our “research presence” using telephone assessments, limiting research contact, compensating participants, and allowing bCBT participants who drop out of treatment to continue with research follow-up assessments.

All analyses for the study will occur exclusively at the Houston HSR&D CoE under the direction of the study PIs ([name] and [name]) and study data analyst ([name]).

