## DATA ANALYSIS PLAN

### Primary aim: Anxiety and Quality of Life differ as a function of bCBT for anxiety vs. EUC

All analyses will be done on an intention-to-treat basis, and participants will be analyzed in the group to which they were randomized. We will first determine whether participants randomized to the two study arms differed on baseline characteristics, age, race, gender, medical or mental health comorbidities, and anxiety. Chi-square tests will be used for categorical variables and t-test for continuous and ordinal variables.

We will examine the normality of the distributions of both primary outcomes and will consider transformations such as the log or the inverse. Because we are using an unequal randomization (see sample size section), it is especially important to test the assumption about the homogeneity of the variance of the residuals across the levels of the independent variables. For analyses of our primary outcomes, we will test the homogeneity assumption before testing for differences between the bCBT and EUC groups. If the assumption of equal variances is violated, we will use statistical tests such as the approximate t-test, which uses individual sample variances instead of the pooled variance. In addition, we will obtain Satterthwaite's approximation of the degrees of freedom. For the regression models, we will test whether the residual variances are equal and, if necessary, we will fit unequal variance models to obtain better estimates of the standard errors of the difference between groups. We will calculate the absolute differences in outcome measures between baseline and 12-month follow-up and the effect sizes of the bCBT group compared with EUC. We will also examine effect sizes for the bCBT group baseline vs. post-treatment and 8-month follow-up.

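### A homogeneity pre-test chooses between pooled and arm-specific variances under a 145:80 split; fixing arm-specific variances in advance is a minor, nearly free improvement

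*Protocol*

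**What the plan says.** Protocol section 5.6 (Data Analysis, primary aim) and the SAP (Primary aim) carry the same rule. Both say that unequal allocation makes equality of variance matter more, and both then make the analysis conditional on a test of it:

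- Protocol, with the same sentence in the SAP: "we will test the homogeneity assumption before testing for differences between the bCBT and EUC groups".
- SAP, on the consequence: "If the assumption of equal variances is violated, we will use statistical tests such as the approximate t-test". Satterthwaite degrees of freedom go with it.
- Protocol, on regression models: "we will test whether the residual variances are equal and, if necessary, we will fit unequal variance models".

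The text does not name the homogeneity test or its significance level. The primary comparison is the time-by-treatment interaction in a random-coefficient mixed model, so the conditional rule for regression models reaches it.

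On allocation, the protocol's Step 2 says "approximately 60% of Veterans will be randomized to bCBT", and Step 3 ends with "The final number of randomized patients equates to 225 (145 bCBT and 80 EUC". That is 145/225 = 64.4% bCBT, a ratio of 1.81 to 1.

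**The concern.** A non-significant homogeneity test does not show that variances are equal. At this trial's size it will often miss a difference large enough to matter. When it misses, the plan reverts to a common variance, and with unequal arms the resulting standard error is biased. It is too small if the smaller arm (EUC) is the more variable, and too large if the larger arm (bCBT) is. The first raises the false-positive rate; the second loses power. Because the pre-test is unnamed, the rule is also not fully specified in advance. What is at stake is modest: a primary test that does not quite hold its stated two-sided .05 level, when an alternative already named in the plan does.

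**Working it through.** **Inputs from the protocol (section 5.6).** Step 3 reproduces from the Step 2 figures of 87 bCBT and 58 EUC: 87 × 1.25 = 108.75, so 109; 109/0.75 = 145.3, so 145; 58/0.75 = 77.3, given as 78 and rounded to 80; total 225. Attrition of 25% leaves 145 × 0.75 = 109 and 80 × 0.75 = 60 evaluable. The test level is two-sided .05 and the effect size is 0.38.

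**Assumptions, because the documents give no figure.** Pre-test: Levene at .05. EUC/bCBT SD ratio: 0.8 to 1.3. Normal data, one time point, independent patients.

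**Why the pooled test goes wrong.** The true variance of the mean difference is s₁²/n₁ + s₂²/n₂. The pooled test in effect uses [((n₁−1)s₁² + (n₂−1)s₂²)/(n₁+n₂−2)] × (1/n₁ + 1/n₂). Take bCBT SD 0.8 and EUC SD 1 (EUC/bCBT ratio 1.25) at 109:60:

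- True: 0.64/109 + 1/60 = 0.02254.
- Pooled: [(108 × 0.64 + 59)/167] × 0.02584 = 0.7672 × 0.02584 = 0.01982.
- The pooled standard error is √(0.01982/0.02254) = 0.938 of the true one, so the critical value is in effect 1.96 × 0.938 = 1.84 and the type I error is about 6.6%.

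With bCBT SD 1.25 and EUC SD 1 (ratio 0.8), the same steps give 0.03102 true and 0.03524 pooled, a standard error 1.066 times too large and a type I error of about 3.7%.

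**How often the pre-test helps.** In simulation at 109:60 with EUC/bCBT ratios of 1.2 to 1.3, Levene rejects in only 31% to 56% of trials. In the trials where it does not reject, the pooled test that follows has a type I error of about 6.5% to 6.9%.

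**Resulting type I error at 109:60 (simulation; pooled values for ratios below 1 from the formula above):**

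| EUC/bCBT SD ratio | Always pooled | Pre-test, then choose | Always unequal-variance |
|---|---|---|---|
| 1.2 to 1.3 | 6.2–7.0% | 5.5–5.7% | about 5% |
| 1.0 | 5.0% | 5.0% | 5.0% |
| 0.8 to 0.9 | 3.7% (at 0.8) to 4.4% (at 0.91) | 4.4–4.6% | about 5% |

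At 145:80, without attrition, the two-stage range is similar: 4.56% to 5.56% with a Levene pre-test.

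**Cost of always using the unequal-variance test.** With equal variances and d = 0.38 (noncentral t, single time point), power is 77.5% pooled against 77.4% at 145:80, and 65.2% against 65.0% at 109:60. These figures compare the two tests; they are not the trial's repeated-measures power. Where bCBT is the more variable (bCBT/EUC ratio 1.25, 145:80), the two-stage rule has 79.1% and the unequal-variance test 80.2%.

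**Does it carry to the primary model?** With complete data at 0, 4, 8 and 12 months, the interaction compares per-patient slopes. The times deviate from their mean by −6, −2, 2 and 6, with squares summing to 80, so each slope has variance (random-slope variance) + (residual variance)/80. Either component can differ by arm. In a balanced random-slope simulation of 1,500 trials with residual SD 1.3 times larger in EUC, type I error was about 6.0% with a common residual variance and 4.4% with arm-specific ones. When only the random-slope variance differed, arm-specific residual variances made no difference (5.7% against 5.6%). The simulation error of each estimate is √(0.05 × 0.95/1500) = 0.6 points, so these runs show direction only.

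**The case against.** The strongest reply is that the plan already deals with this. It names unequal allocation as the reason variance matters, supplies the right tests and models, and states the conditional rule in advance. That stands in part: a reader might infer that the plan ignores unequal variances or leaves the choice open to the analyst, and the text supports neither. Only the trigger is at fault, together with its unnamed test and level.

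Second, most of the calculation is a two-sample comparison, while the primary test is a mixed-model interaction. The rule for regression models is written the same way, and the balanced check points in the same direction. But the mixed model with missing data was not simulated, and neither was its convergence when arm-specific variances are always fitted. The check also shows that arm-specific residual variances alone are not a complete remedy.

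Third, a reader might infer that unequal variances are built into the design, because the protocol assumes a within-provider correlation of .10 in bCBT only, and that arm-specific variances would take care of it. The figures do not support this. With equal within-provider variance, bCBT variance is 1/0.9 = 1.11 times that of EUC, an EUC/bCBT SD ratio of √0.9 = 0.95. That is small and in the conservative direction: treating patients as independent, the two-stage type I error at that ratio is 4.75%. The inflation to 5.7% needs EUC to be clearly the more variable arm, which nothing in the documents indicates. Nor does the unequal-variance test account for correlation between patients of the same provider. With 25 providers and a correlation of .10 simulated in bCBT, type I error was about 6.1% to 6.2% pooled and 6.5% to 6.6% with the unequal-variance test.

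**Conclusion.** The point holds as a minor improvement. Under the assumed Levene pre-test at .05, SD ratios of 0.8 to 1.3 and 109:60 evaluable, the planned rule gives a type I error of roughly 4.4% to 5.7%, and exactly the nominal level if variances are equal. Always using arm-specific variances in the t-test holds about 5% throughout. A reader might infer that the primary result is at serious risk of a false positive; a departure of well under one percentage point, resting on SD ratios that the documents do not supply, does not support that. For the mixed model, the direction is shown only in a small balanced check, and its size in the planned analysis is not established.

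**What to change.** In Protocol section 5.6 and the matching SAP paragraphs, remove the homogeneity test as the trigger for the choice of analysis. State instead that:

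- t-tests on the primary outcomes always use the unequal-variance form with Satterthwaite degrees of freedom;
- the primary mixed models are specified in advance with arm-specific variances, for the residuals and, where estimable, for the random slopes;
- if that model does not converge, a named simpler model with a common variance is used.

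Variances by arm can still be reported descriptively. The cost is a few sentences, 0.1 to 0.2 points of power in the t-tests if variances are equal, and one or a few extra variance parameters in the mixed models. Provider clustering needs its own treatment and should not be presented as covered by this change.
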